6.1.4. Handling of Dropouts or Missing Data

6.1.4.1. Imputation of Missing Data

Any subject who prematurely withdraws from the study will have their last available data assigned to an analysis window as described in Section 6.1.5.

For the primary efficacy endpoint of S-IGA score, the primary analysis will impute missing values using a regression-based multiple imputation model. This is a three step process.

1. The first step is to understand the pattern of missingness. In order to perform the multiple imputation, a monotone missing pattern has to be achieved. For example, if there exists values for baseline and Week 8 visits, but missing values for the Week 2 or 4 visits, Markov-Chain Monte-Carlo (MCMC) method will be used to impute the small amount of missing data that may be missing at the intermediate visits that is required to make the missing data pattern monotone before applying the multiple imputation algorithm. This method uses a non-informative Jeffreys prior to derive the posterior mode from the expectation-maximization (EM) algorithm as the starting values for the MCMC method. MCMC method will use seed of 34978264. The S-IGA score will be treated as a continuous variable for this step. To avoid values that could not be observed in practice, imputed values will be constrained to be integers in the range of 0 to 4.
 - a. The table below will determine the number of datasets to be imputed in this step. Determine the proportion of datapoints with non-monotone pattern across all visits and subjects which could be derived as a percentage of number of nonmonotone data points/total number of expected data points.

This can be determined as $\frac{\text{number of non monotone visits}}{\text{total number of visits across all subjects}} * 100$

Non-monotone Missing Data	Number of Imputed Datasets
≤ 2%	1
> 2% to ≤ 5%	3
> 5%	10

2. Once the monotone pattern is achieved, the next step is to implement the imputation algorithm. For this, the Predictive Mean Matching method (PMM) will be used. This method is particularly helpful if the normality assumption is violated. For subjects with complete data up to a particular visit, a PMM model will be fit that includes the outcome at that visit as the dependent variable and as independent variables, S-IGA score outcomes at previous visits, treatment group, and country using a seed of 51192215. This process will be repeated 25 times, resulting in a total of 25 to 250 complete analysis

datasets, depending on the number of imputed monotone datasets that are required. The seed may be changed after unblinding in case of any issues with the imputation process, and it will be documented in the CSR if any change is required.

3. For each completed dataset, compute the necessary derived variables. The dichotomous success rate (clear or almost clear with at least a 2-point change from baseline) will be derived. The results obtained will be analyzed using the Cochran-Mantel-Haenszel (CMH) analysis for each of the complete analysis data sets stratified by baseline S-IGA score category, baseline B-IGA score category, and country. The results will be combined into one multiple imputation inference (odds ratio, associated CI, and *P* value) using PROC MIANALYZE as illustrated⁴.

This approach to imputation should be superior to other strategies such as carrying forward the last available observation, which may yield unrealistic imputed values. Also, the use of multiple imputation avoids the problem of artificially increasing power through data imputation associated with single-imputation methods because it accounts for the uncertainty associated with the imputation. Other missing data will not be imputed, with the exception of incomplete dates as described in Section 6.1.8. For responder analyses, missing data will be treated as a nonresponse with the exception of S-IGA. Only observed data will be summarized using descriptive statistics.

The SAS pseudo code for the multiple imputation process is listed below:

Step 1:

```
proc mi data=example seed=34978264 nimpute=XX round=1 out=example_1;  
  mcmc impute=monotone;  
  var <baseline score> ..... <visit8 score>;  
run;
```

Step 2:

```
proc mi data=example_1 seed=51192215 nimpute=XX out=example_2;  
  class <treatment> <country>;  
  monotone regpmm(<baseline score> ..... <visit8 score>);  
  var <treatment> <country> <baseline score> ..... <visit8 score>;  
run;
```

XX will be determined based on the proportion of missing data across visits.

Step 3: This step involves running CMH test stratified by baseline S-IGA score category, baseline B-IGA score category, and country on each completed dataset and combining the results using PROC MIANALYZE.

```
proc freq data=example noprint;  
  by <imputationnumber> <visit> ;  
  tables <country> * <BL S-IGA cat> * <BL B-IGA cat> * <treatment> *  
    <outcome> / cmh alpha=0.05;  
  output out=example_stat cmh;  
run;
```

In order to apply PROC MIANALYZE, normalizing transformations have to be applied to odds ratio. *P* values are obtained using Wilson Hilferty transformation as illustrated⁴.

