3.1. Overall Design

This is a parallel group, double blind, vehicle-controlled study in which roflumilast foam 0.3% or vehicle foam is applied QD x 8 weeks to adolescent and adults with scalp and body psoriasis of at least mild severity (S-IGA and B-IGA with a score of at least “2”), involving up to 25% body surface area (BSA) (scalp and body, not including palms/soles).

Approximately 300 subjects will be enrolled. After having met all inclusion criteria, and none of the exclusion criteria, subjects will be randomized in a 2:1 ratio to roflumilast foam 0.3% QD or vehicle foam QD, which will be applied to all psoriasis lesions (including the scalp, face, trunk, and intertriginous areas; palms and soles will be treated but will not be counted towards any measurements of efficacy). Screening will be for up to 4 weeks followed by an 8-week Treatment Phase, with a Follow-up Visit 1 week after last dose. The anticipated maximum duration of subject participation is approximately 13 weeks.

Subjects will have to apply the study drug once a day in the evening, with the exception of Day 0, Week 2 (Visit 3), and Week 4 (Visit 4), when the study drug is applied at the study site in the morning. Participants have to record the date and time each dose has been applied with details including missed doses and any additional comments.

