3.2. Sample Size and Power

There are approximately 300 subjects planned for this study. Approximately 200 subjects will receive roflumilast foam 0.3% QD; approximately 100 subjects will receive vehicle foam QD. The sample size was selected to provide an adequate number of subjects to compare the efficacy of roflumilast treatment to vehicle and to provide an adequate number of subjects needed for a safety database.

This sample size provides 96% power at the $\alpha=0.05$ level to detect a 22.4% difference between treatment groups for S-IGA Success at Week 8 using a 2-sided Chi-squared test. The results from a recent phase 2b study (ARQ-151-201) of roflumilast cream compared to vehicle treatment were used to estimate the treatment difference, and it is assumed that the S-IGA response in the present study are similar to IGA responses seen with roflumilast cream. Specifically, in the phase 2b trial, 32.2% of subjects reported IGA success in the roflumilast cream 0.3% group and 9.8% of subjects reported IGA success in the vehicle group.

The number of subjects to be enrolled will also provide sufficient power for most secondary

endpoints.

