For this study, the primary estimand is the odds of achieving S-IGA success at 8 weeks; that is, the ratio of the odds of achieving S-IGA success at 8 weeks roflumilast foam 0.3% relative to the odds of success at 8 weeks of using a matching vehicle cream. In the course of the 8-week randomized treatment period, subjects may be exposed to possible known or unknown intercurrent events that could possibly impact the estimand, such as treatment discontinuation due to a specific adverse effect or perhaps a lack of effect. The “Treatment Policy Strategy” has been adopted for handling all known or unknown intercurrent events in this study. To this end, the ITT principle will serve as the analytical basis for interpreting the estimand. In other words, the odds ratio of achieving S-IGA success for roflumilast foam 0.3% relative to vehicle at 8 weeks will be evaluated regardless of the occurrence of any such intercurrent event. This estimand shall be estimated using the CMH approach. This approach produces an estimate that is the combined odds ratio resulting from adjusting for the possible effects of 3 classification factors: country, baseline S-IGA category (2 vs. ≥ 3) and baseline B-IGA category (2 vs. ≥ 3).

Categorical Data Analysis

The primary efficacy endpoint is success in S-IGA of disease severity, defined as an S-IGA of “Clear” or “Almost Clear” plus a 2-grade improvement from baseline at Week 8.

The primary endpoint will be analyzed using a CMH test stratified by country, baseline S-IGA category, and baseline B-IGA category. Statistical significance will be concluded at the 5% significance level (2-sided) or less, as discussed in Section 6.1.3. Odds ratios and 95% CIs for the odds ratios will be provided. Additionally, the 95% Wilson CIs for proportion of successes in each treatment group will be presented.

For the primary analysis, missing S-IGA scores will be imputed using multiple imputation as described in Section 6.1.4.1. These imputations will result in a minimum of 25 to a maximum of 250 complete analysis datasets, depending on the number of imputed monotone datasets required. The CMH analyses will be performed separately for each of the complete analysis data sets, and the results will be combined into one multiple imputation inference (estimated treatment effect and associated CI and *P* value). As a sensitivity analysis, the above described CMH test will be performed on the nonimputed data.

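### The SAP allows the primary-analysis imputation seed to be changed after unblinding, on an undefined trigger and with no pre-named replacement

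*SAP*

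**What the plan says.** SAP 8.1.1 bases the primary result on imputed data: "For the primary analysis, missing S-IGA scores will be imputed using multiple imputation as described in Section 6.1.4.1". The test is stratified CMH, two-sided at 5%, and SAP 6.1.3 makes its significance the entry condition for B-IGA success and, through that, for both secondary families.

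SAP 6.1.4.1 gives each imputation step its own seed. Step 1 (MCMC, to reach a monotone pattern) uses 34978264. Step 2 (predictive mean matching) conditions on earlier S-IGA scores, "treatment group, and country using a seed of 51192215". Step 2 makes 25 draws from each of 1, 3 or 10 monotone datasets, according to how much missingness is non-monotone, so the analysis pools 25, 75 or 250 completed datasets.

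Step 2 then ends with: "The seed may be changed after unblinding in case of any issues with the imputation process". The same sentence requires any change to be documented in the CSR. The SAP does not say what counts as an issue, which seed follows, who decides, how many changes are allowed, or whether a result already obtained with the specified seed must be shown. It does not say whether the permission covers the Step 1 seed. The tipping-point code in 6.1.4.2 reuses 51192215 and is not mentioned.

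**The concern.** Multiple imputation is a random procedure, so the pooled p-value depends slightly on the seed. Fixing the seed in advance removes that freedom, and this sentence gives it back once treatment codes are known. Reporting a change in the CSR makes it visible but does not show that it was made independently of the result.

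No other rule in the SAP closes the gap. The provision in SAP Section 1 for a blinded statistician covers only amendments after unblinding for an interim analysis, and SAP 4.2 plans no interim efficacy analysis. A seed change would not be an amendment in any case, because the SAP already permits it. At stake is whether a borderline primary result, and the secondary testing that depends on it, could be defended as fully pre-specified.

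**Working it through.** **The plan's own figures.** The documents give no figure for seed variability, so there is none to reproduce. The figure that helps with scale is the power calculation in SAP 3.2, which states 96% power. Its inputs are "32.2% of subjects reported IGA success in the roflumilast cream 0.3% group and 9.8% of subjects reported IGA success in the vehicle group", with about 200 and 100 subjects. The pooled two-proportion formula with these inputs gives 99.7%; 96% would correspond to about 66 vehicle and 132 active subjects. That mismatch is a separate matter, and nothing below depends on it.

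**Seed variability.** Let B be the between-imputation variance, T the total variance and M the number of completed datasets. Changing only the seed moves the pooled estimate with variance B/M. Dividing by T, and using FMI ≈ B/T, the seed-to-seed SD of the pooled z is about √(FMI/M).

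Assumptions, none of them from the documents:
- FMI is 10-20%.
- In the worst case ten seeds are tried and the most favourable is kept. The expected maximum of ten standard normal values is 1.54.

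| FMI | M | SD of z | Gain from best of ten | p-value brought to 0.05 |
|---|---|---|---|---|
| 10% | 25 | √(0.10/25) = 0.063 | 1.54 × 0.063 = 0.097 | 0.062 (z = 1.96 − 0.097) |
| 20% | 25 | √(0.20/25) = 0.089 | 1.54 × 0.089 = 0.138 | 0.068 (z = 1.96 − 0.138) |
| 10% | 250 | √(0.10/250) = 0.020 | 1.54 × 0.020 = 0.031 | 0.054 |
| 20% | 250 | √(0.20/250) = 0.028 | 1.54 × 0.028 = 0.044 | 0.055 |

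The formula treats the datasets as independent. At 75 or 250 they are nested within 3 or 10 monotone datasets, so those figures are approximate.

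**Check by simulation.** The SAP procedure was simulated with 300 subjects at 2:1, sequential predictive mean matching, stratified CMH, and pooling of both the log odds ratio and the Wilson-Hilferty-transformed statistic. Week 8 missingness of 5-20%, the correlation between visits, four strata, five matching donors and a baseline S-IGA of 3 or 4 were assumed.
- In trials with p near 0.05, the seed-to-seed SD of p at M = 25 was about 0.004 at 5% missing, 0.006-0.007 at 10% and 0.009-0.010 at 20%. At M = 250 it was about 0.001-0.003.
- Of these borderline trials at M = 25, 14-52% had seeds on both sides of 0.05 among 20 tried.
- Under the null at M = 25, going from one seed to the best of ten raised the type I error from 0.039-0.048 to 0.055-0.056 (log odds ratio) and from 0.051-0.056 to 0.063-0.069 (Wilson-Hilferty). Within each setting the rise was about 0.8 to 1.8 percentage points. The Monte Carlo standard error is about 0.5 point per rate.

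**At the planned effect.** The pooled response rate is (2 × 0.322 + 0.098)/3 = 0.247. The expected z is 0.224/√(0.247 × 0.753 × (1/200 + 1/100)) = 4.24. Losing 20% of the information leaves 4.24 × √0.8 = 3.79, which is (3.79 − 1.96)/0.089 ≈ 20 seed SDs above the critical value even at M = 25. In simulation at 10-20% missing, at most 1% of trials could change significance by seed.

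**The case against.** The permission is conditional on a problem with the imputation and on a change being required, which most naturally means that the procedure failed to run. Treatment is a covariate in the Step 2 model, so the production run needs the real codes and must follow unblinding; the timing needs no other explanation. Any change must be disclosed. SAP 8.1.1 also plans CMH and GEE analyses on non-imputed data, and 6.1.4.2 a tipping-point analysis, against which a result that rested on the seed would look fragile. Finally, 25 datasets is the minimum; above 2% non-monotone missingness there are 75 or 250, and the seed matters less.

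Most of this stands. A reader might infer that the SAP authorises picking a seed by its result, or that it plans for several seeds to be tried. The documents do not support that: no text links the change to the p-value, and ten undisclosed tries would breach the SAP's own documentation rule. The best-of-ten figures are an upper illustration and do not describe planned conduct. What remains is that the trigger is undefined and the replacement open. The sensitivity analyses help to reveal a fragile result, but they do not fix which primary p-value is reported.

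**Conclusion.** The point holds as a minor drafting gap: a parameter of the primary p-value can be changed with treatment codes known, without a stated criterion or a pre-named replacement. If FMI is 10-20%, the seed-to-seed SD of z is about 0.06-0.09 at 25 datasets and 0.02-0.03 at 250, and the worst-case gain from ten seeds is about 0.10-0.14 and 0.03-0.04 respectively.

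These figures rest on assumed missingness and on a generic pooled z; the SAP takes its P value from the Wilson-Hilferty transformation, for which the simulation gave effects of similar size. It would be wrong to conclude that the primary result is materially at risk. The choice matters only for a p-value close to 0.05, and the planned effect lies far from that boundary.

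**What to change.** Replace the sentence in SAP 6.1.4.1 with:

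> The seeds (34978264 for MCMC, 51192215 for PMM) will not be changed after unblinding, except that if PROC MI fails to run to completion the next seed in this pre-specified ordered list is used: (two or three seeds per step). Any such use is reported in the CSR, with the original-seed result where one was produced, and is applied to the tipping-point code as well.

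Before unblinding, run the imputation program on the locked data with dummy treatment codes. This should expose most technical failures. It cannot exclude one that appears only with the real codes, which is why the ordered list is needed as well.

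Set the Step 2 NIMPUTE to at least 100. Since √(25/100) = 0.5, this halves the seed effect relative to 25. The dataset counts in 6.1.4.1 and 8.1.1 then become 100 to 1,000.

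The cost is one replaced sentence with the matching counts, one blinded run, and slightly more computing time.

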Sensitivity analyses of the primary endpoint will also be performed using the original (nonimputed) dataset. These will include a repeated measures logistic regression model (GEE) with S-IGA success as the dependent variable and treatment, country, visit, and baseline S-IGA score as the independent variables.

Achievement of a score of clear will also be analyzed using the CMH test, on nonimputed data.

A tipping point analysis will be performed as described in Section 6.1.4.2. For the tipping point analysis, a figure will be provided that displays the P values in the analysis plotted against the range of shift parameters; included in this figure will be the shift parameters and P values for the range of shift parameters to provide information on where the analysis tips from significant to non-significant.

Subgroup Analyses – Observed Data

For the primary endpoint of IGA success (S-IGA of “Clear” or “Almost Clear” plus a 2-grade improvement from baseline at Week 8), the CMH analysis will be performed on the following subgroups, using observed data:

- Topical Corticosteroids – Naïve Subjects
- Topical Vitamin D Derivatives – Naïve Subjects
- Psoriasis involvement on the knee and/or elbow
- Subjects who achieved both S-IGA and B-IGA success at Week 8
- By Study Site

Subgroup Analyses – Multiple Imputation Data

For the primary endpoint of IGA success (S-IGA of “Clear” or “Almost Clear” plus a 2-grade improvement from baseline at Week 8), the CMH analysis will be performed on the following subgroups, using multiple imputation data:

- Baseline S-IGA = 3
- Baseline S-IGA = 4
- Age Category = 12-17 years
- Age Category = ≥ 18 years
- Subjects who achieved both S-IGA and B-IGA success at Week 8

Continuous Data Analysis

Analysis of change from baseline in S-IGA scores at Weeks 2, 4, 8, and 9 will be performed using descriptive summaries (mean, median, inter-quartile range) by treatment group and study visit. These descriptive statistics will also be presented based on the multiple imputation data.

All Analyses

All other missing data for all other analyses and summaries will remain missing and will not be imputed. All weeks will be included in these analyses, although only Week 8 using the ITT population will be included in the testing strategy.

The primary efficacy analysis will be based on ITT population, and all of the above analyses will be repeated for the mITT population.

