8.2.1. Body Investigator Global Assessment (B-IGA)

The scale, grade, and description for the B-IGA is identical to the S-IGA, as discussed in Section 8.1.

Achievement of a B-IGA score of “clear” or “almost clear” PLUS a 2-grade improvement from baseline at Weeks 2, 4, 8, and 9 will be analyzed similar to the primary efficacy endpoint using CMH test stratified by country, baseline S-IGA category, and baseline B-IGA category, with the exception that missing data will not be replaced (i.e., observed data). Odds ratios and 95% CIs of the odds ratios will be provided. Additionally, the 95% Wilson CIs for proportion of successes in each treatment group will be presented. In addition, the number and percentage of subjects in each category will be summarized by treatment and visit. Only the Week 8 results using the ITT population will be included in the testing strategy.

Analysis of change from baseline in B-IGA scores at Weeks 2, 4, 8, and 9 will be performed using descriptive summaries (mean, median, inter-quartile range) by treatment group and study visit.

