8.2.2. Psoriasis Scalp Severity Index (PSSI)

The PSSI is used to measure the severity of psoriasis, combining the assessment of the severity of scalp lesions and the area of scalp affected into a single score ranging from 0 (no disease) to 72 (maximal disease). The PSSI score will be analyzed as follows:

- Change and percent change from baseline to Weeks 2, 4, 8, and 9 in the PSSI will be analyzed using descriptive summaries and an analysis of covariance (ANCOVA) with terms for country, baseline S-IGA category, and baseline B-IGA category, and baseline PSSI score as a covariate. Statistical comparisons between the treatment groups will be obtained using contrasts. The least-squares (LS) means, standard errors, 95% CIs, and *P* values will be presented.
- Frequencies and percentages of subjects achieving PSSI-50, PSSI-75, PSSI-90, and PSSI-100 will be presented by study week and treatment group. Additionally, these endpoints will be analyzed similar to the primary efficacy endpoint using a CMH test stratified by country, baseline S-IGA category, and baseline B-IGA category, on observed data. Only the PSSI-75 and PSSI-90 at Week 8 using the ITT population will be included in the testing strategy. Odds ratios and 95% CIs of the odds ratios will be provided. Additionally, the 95% Wilson CIs for proportion of successes in each treatment group will be presented.
- Time to achieving PSSI-50, PSSI-75, and PSSI-90 will be summarized using Kaplan-Meier methods and the difference between treatment groups evaluated using the log-rank statistic, and 95% CIs of the median for each treatment group will be presented. In addition, a Cox proportional hazards model that includes the stratification factors will be run and the hazard ratio and associated 95% Wald CIs will be presented. Time to achieving PSSI-50 using the ITT population will also be included in the testing strategy. Time to achieving PSSI-75 or PSSI-90 using the ITT population will not be included in the testing strategy, but will be considered as a supportive analysis.

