8.2.3. Scalp Itch – Numeric Rating Scale (SI-NRS)

The SI-NRS scale ranges from 0 to 10 with 0 being “no scalp itch” and 10 equaling “worst scalp itch imaginable.” This will be determined by asking the subject’s assessment of worst scalp itch over the past 24 hours. The SI-NRS will be analyzed as follows:

- Change and percent change from baseline to Weeks 2, 4, and 8 in SI-NRS will be analyzed using descriptive summaries and an ANCOVA with terms for country, baseline S-IGA category, and baseline B-IGA category, and baseline SI-NRS score as a covariate. Statistical comparisons between the treatment groups will be obtained using contrasts. The LS means, standard errors, 95% CIs, and *P* values will be presented.
- In subjects with a baseline SI-NRS score ≥ 4 , achievement of a ≥ 4 -point improvement from baseline in SI-NRS score at Weeks 2, 4, and 8 will be analyzed using CMH tests stratified by country, baseline S-IGA category, and baseline B-IGA similar to the primary analysis above, with the exception that missing data will not be replaced. Odds ratios and 95% CIs of the odds ratios will be provided. Additionally, the 95% Wilson CIs for proportion of successes in each treatment group will be presented. This will be summarized using SPRU-ITT and SPRU-mITT populations.

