Odds Ratio (95% CI) [3]	X.XX (X.XX, X.XX)	
P value [3]	X.XXXXX	

Repeat for all Week 4, Week 8, and Week 9.

Abbreviations: B-IGA = body investigator global assessment; CI = confidence interval; S-IGA = scalp investigator global assessment.
Note: Percentages are n/Number of subjects in the ITT population within planned treatment at each visit*100. Baseline is the last non-missing measurement taken before the first application of study drug.
[1] S-IGA Success ("Yes") is defined as an S-IGA score of "Clear" or "Almost Clear" plus a ≥2-grade improvement from baseline; "No" otherwise.
[2] 95% CIs for "Yes" are obtained using Wilson method.
[3] The odds ratio, 95% CI, and P value are obtained from Cochran Mantel Haenszel test (stratified by country, baseline S-IGA category, and baseline B-IGA category) comparing roflumilast foam 0.3% to vehicle. Reference Listings: 16.2.6.1, 16.2.6.2

Table 14.2.1.5.2

Summary of Scalp Investigator Global Assessment (S-IGA) Grades and Success by Study Visit – Observed Data
Categorical Results

ITT Population - Topical Corticosteroids - Naïve Subjects

(Same shell as Table 14.2.1.5.1; add 16.2.4.2 to reference listings; change “Percentages” footnote to be “Percentages are n/Number of subjects in the ITT population that are topical corticosteroids – naïve subjects within planned treatment at each visit*100.”)

Table 14.2.1.5.3

Summary of Scalp Investigator Global Assessment (S-IGA) Grades and Success by Study Visit – Observed Data
Categorical Results

ITT Population - Topical Vitamin D Derivative - Naïve Subjects

(Same shell as Table 14.2.1.5.1; add 16.2.4.2 to reference listings; change “Percentages” footnote to be “Percentages are n/Number of subjects in the ITT population that are topical vitamin D derivative – naïve subjects within planned treatment at each visit*100.”)

Table 14.2.1.5.4

Summary of Scalp Investigator Global Assessment (S-IGA) Grades and Success by Study Visit – Observed Data
Categorical Results

ITT Population - Subjects with Psoriasis Involvement on the Knee and/or Elbow

(Same shell as Table 14.2.1.5.1; add 16.2.4.2 to reference listings; change “Percentages” footnote to be “Percentages are n/Number of subjects in the ITT population that have psoriasis involvement on the knee and/or elbow within planned treatment at each visit*100.”)

Table 14.2.1.5.5

Summary of Scalp Investigator Global Assessment (S-IGA) Grades and Success by Study Visit – Observed Data
Categorical Results

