Study Visit Category/Statistic	Roflumilast Foam 0.3% (N=XX)	Vehicle (N=XX)
Week 2	XX	XX
S-IGA Clear [1]		
Yes	XX (XX.X%)	XX (XX.X%)
95% CI [2]	(X.XX, X.XX)	(X.XX, X.XX)
No	XX (XX.X%)	XX (XX.X%)
Odds Ratio (95% CI) [3]	X.XX (X.XX, X.XX)	
P value [3]	X.XXXXX	

Repeat for all Week 4, Week 8, and Week 9.

Abbreviations: CI = confidence interval; S-IGA = scalp investigator global assessment.
Note: Percentages are n/Number of subjects in the ITT population within planned treatment at each visit*100. Baseline is the last non-missing measurement taken before the first application of study drug.
[1] S-IGA Clear (“Yes”) is defined as an S-IGA score of “Clear”; “No” otherwise.
[2] 95% CIs for “Yes” are obtained using Wilson method.
[3] The odds ratio, 95% CI, and P value are obtained from Cochran Mantel Haenszel test (stratified by country, baseline S-IGA category, and baseline B-IGA category) comparing roflumilast foam 0.3% to vehicle.
Reference Listing: 16.2.6.1

Table 14.2.1.12
Summary of Scalp Investigator Global Assessment (S-IGA) – Score of Clear – Observed Data
mITT Population

(Same as table shell 14.2.1.11)

Figure 14.2.1.14
Plot of Scalp Investigator Global Assessment (S-IGA) Tipping Point Analysis
P Values vs Shift Parameters
mITT Population

(Programming note: Same as figure shell 14.2.1.13)

Table 14.2.2.1
Summary and Change from Baseline in Body Investigator Global Assessment (B-IGA) Grades by Study Visit
ITT Population

(Programming note: Same as table shell 14.2.1.1; update reference listing to Reference Listing: 16.2.6.2; Update any instances of S-IGA to B-IGA)

Table 14.2.2.2
Summary and Change from Baseline in Body Investigator Global Assessment (B-IGA) Grades by Study Visit
mITT Population

(Programming note: Same as table shell 14.2.1.1; update reference listing to Reference Listing: 16.2.6.2; Update any instances of S-IGA to B-IGA)

Table 14.2.2.3
Summary of Body Investigator Global Assessment (B-IGA) Grades and Success by Study Visit
Categorical Results
ITT Population

(Programming note: Same as table 14.2.1.5; update reference listing to Reference Listings: 16.2.6.1, 16.2.6.2; Update any instances of S-IGA to B-IGA)

Table 14.2.2.4
Summary of Body Investigator Global Assessment (B-IGA) Grades and Success by Study Visit
Categorical Results
mITT Population

(Programming note: Same as table 14.2.1.5; update reference listing to Reference Listing: 16.2.6.2; Update any instances of S-IGA to B-IGA)

Table 14.2.3.1

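### Six of the nine alpha-controlled secondary endpoints, including the B-IGA gate, carry two incompatible missing-data rules, and neither is the protocol's multiple imputation

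*SAP*

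**What the plan says.** After describing multiple imputation for S-IGA, SAP 6.1.4.1 gives two consecutive sentences: "Other missing data will not be imputed, with the exception of incomplete dates as described in Section 6.1.8", then "For responder analyses, missing data will be treated as a nonresponse with the exception of S-IGA".

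The endpoint sections read differently:

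- **SAP 8.2.1, B-IGA success:** analysed like the primary, "with the exception that missing data will not be replaced (i.e., observed data").
- **SAP 8.2.2, PSSI-75 and PSSI-90:** the CMH test is run "on observed data. Only the PSSI-75 and PSSI-90 at Week 8 using the ITT population will be included in the testing strategy".
- **SAP 8.2.3, SI-NRS response:** "similar to the primary analysis above, with the exception that missing data will not be replaced".
- **SAP 8.1.1, closing paragraph:** "All other missing data for all other analyses and summaries will remain missing and will not be imputed".

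SAP 6.1.3 tests B-IGA success at Week 8 at 5% once S-IGA is significant. Only if B-IGA is also significant is alpha split into 0.03 and 0.02 for the remaining secondary endpoints.

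Protocol 6.3.1 specifies multiple imputation for missing S-IGA and B-IGA scores. The protocol synopsis gives multiple imputation for continuous secondary endpoints and says binary ones follow the primary analysis. Protocol 6.3.2 repeats the CMH and ANCOVA methods without mentioning imputation. SAP Section 10 lists added populations, removal of the per-protocol population, and added endpoints and analyses. It does not mention missing data.

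**The concern.** A subject with no Week 8 B-IGA cannot be both left out of the denominator and counted as a failure. S-IGA is the only exception named in 6.1.4.1, so every other responder endpoint falls under non-response there and under observed data in Section 8.2. With both rules in force, the confirmatory result for the gate could be chosen after the data are seen, and that result decides whether any other secondary endpoint is tested at all.

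The second part is that both rules abandon the protocol's method for B-IGA without declaring it. SAP 6.1.4.1 itself argues that multiple imputation is better than simpler strategies, yet gives no reason for dropping it at the gate.

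Some Week 8 gaps are likely: SAP 6.2 states that B-IGA and PSSI cannot be collected remotely, and missed pandemic visits led to the mITT population.

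**Working it through.** **Count of endpoints (SAP 2.2.2.2 and 6.1.3).** The alpha-controlled secondary endpoints are B-IGA W8; PSSI-75 W8; time to PSSI-50; PSD W8; PSD W4; PSSI-90 W8; and SI-NRS W8, W4 and W2. That is nine. The responder endpoints among them are B-IGA, PSSI-75, PSSI-90 and three SI-NRS, which makes six. The other three are a time-to-event endpoint and two changes in PSD score. For PSD the SAP is internally consistent; its only issue is the undeclared departure from the synopsis.

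**Do the table shells settle it?** They lean to observed cases. The B-IGA success table is "Same as table 14.2.1.5; update reference listing to Reference Listings: 16.2.6.1, 16.2.6.2; Update any instances of S-IGA to B-IGA", and the shell it re-uses is labelled observed data, with "Percentages are n/Number of subjects in the ITT population within planned treatment at each visit*100". The PSSI and SI-NRS shells use the same by-visit denominators. But their footnotes define every subject not meeting the criterion as a No, which leaves the non-response reading open.

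**Size at the gate.** The plan gives no figure for this. Inputs are 200 active and 100 vehicle subjects and 32.2% vs 9.8% (SAP 3.2; these are S-IGA planning rates, assumed here for B-IGA). All missing rates, and the 32% vs 20% scenario, are assumptions.

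Expected responders are x = p × N × (1 − m), where m is the missing fraction. Observed data divides x by N(1 − m); non-response divides x by N. The test is z = (pA − pV) / √[p̄(1 − p̄)(1/nA + 1/nV)], two-sided at 0.05.

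Worked case, 32% vs 20%, missing 20% active and 10% vehicle:

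- x is 0.32 × 160 = 51.2 active and 0.20 × 90 = 18 vehicle.
- Observed data: 51.2/160 − 18/90 = 0.320 − 0.200 = 0.120; p̄ = 69.2/250 = 0.2768; SE = 0.0590; z = 2.04; p = 0.042.
- Non-response: 51.2/200 − 18/100 = 0.256 − 0.180 = 0.076; p̄ = 69.2/300 = 0.2307; SE = 0.0516; z = 1.47; p = 0.141.

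| Rates | Missing, active/vehicle | Observed data | Non-response | Gate call |
|---|---|---|---|---|
| 32.2 vs 9.8 | 10/10 | 22.4 points, OR 4.4, p<0.001 | 20.2 points, OR 4.2, p<0.001 | same |
| 32.2 vs 9.8 | 20/5 | 22.4 points, OR 4.4, p<0.0001 | 16.45 points, OR 3.4, p=0.0008 | same |
| 32.2 vs 9.8 | 30/5 | p<0.0001 | p=0.005 | same |
| 32 vs 20 | 5/5 | p=0.033 | p=0.035 | same |
| 32 vs 20 | 10/10 | p=0.038 | p=0.042 | same |
| 32 vs 20 | 20/20 | p=0.051 | p=0.060 | same |
| 32 vs 20 | 15/10 | p=0.040 | p=0.079 | opposite |
| 32 vs 20 | 20/10 | p=0.042 | p=0.141 | opposite |
| 32 vs 20 | 10/20 | p=0.047 | p=0.015 | same |

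Non-response is not always the stricter rule. With about 24% vs 14% and 5%/15% missing, observed data gives 46/190 vs 12/85, p = 0.058; non-response gives 46/200 vs 12/100, p = 0.023.

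**Where the calls part.** With the active rate stepped by 0.1 point, the calls are opposite for observed-data differences of:

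- 11.4–11.5 points (vehicle 20%, missing 10/10);
- 11.6–15.4 points (vehicle 20%, missing 20/10);
- 9.5–11.7 points (vehicle 9.8%, missing 20/10), about half the planned 22.4.

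**Chance of opposite calls.** This was simulated with 100,000 trials per scenario, missingness independent of response within arm, and CMH over eight strata (assumed country split 70/30, baseline S-IGA = 2 in 10%, baseline B-IGA = 2 in 25%, equal response rates across strata). The results are 0.4% (planning rates, 10/10), 4.6% (planning rates, 20/5), 6.3% (32% vs 20%, 10/10) and 22% (32% vs 20%, 20/10). Unstratified tests give 0.35%, 4.4%, 6.2% and 22.8%. This measures disagreement between the rules, not bias in either.

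**The case against.** The strongest reply is that the specific section governs the general one. SAP 8.2 is endpoint-specific, the shells lean the same way, and observed data is evidently what was meant. As a reading of intent that is probably right, but no precedence is written. If it is right, the non-response sentence governs none of the confirmatory endpoints and should go.

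A narrower reply is that 8.2.3 says only that missing SI-NRS data are not replaced, which might coexist with counting them as failures. That is a fair literal point. But 8.2.1 uses the same phrase and explains it as observed data, so the conflict extends to SI-NRS by the SAP's own usage. The closing line of 8.1.1 sits in the S-IGA section and is weaker support.

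On the protocol, multiple imputation is explicit only for B-IGA among the six. For PSSI and SI-NRS it is inferred from the reference back to the primary analysis, and for PSD it rests on the synopsis alone. This limits the departure claim but leaves it intact at the gate. The SAP also cites protocol Amendment 1.0, while the protocol supplied is Amendment 2; the Amendment 2 change list names no change to 6.3.1 or 6.3.2.

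On impact, the reversals need an effect near the significance threshold and, in practice, unequal missingness, and nothing in the documents suggests that missingness differs by arm. Early-termination values from Days 43 to 61 can fill Week 8 (SAP 6.1.5), and SI-NRS can be collected remotely. These points stand and limit the severity. The mITT repeat does not resolve the conflict, because only the ITT result enters the testing strategy.

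**Conclusion.** The concern holds. Six of the nine alpha-controlled secondary endpoints are under two rules that cannot both apply, and the B-IGA gate also departs from the protocol's stated method without a Section 10 entry. At the planning rates the choice changes the estimate (22.4 vs 16.45 points at 20/5 missing) but not the gate call. With an assumed 12-point effect and 20/10 missing it reverses the call on expected counts and produces opposite calls in about 22% of simulated trials; at planning rates with 10/10 missing the figure is 0.4%. All missing rates, stratum sizes and response rates other than 32.2% and 9.8% are assumptions. The primary analysis is unaffected. This should be fixed before unblinding, but it does not threaten the trial's main conclusion.

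**What to change.** Before unblinding:

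- State one confirmatory missing-data rule for each endpoint, in the same terms in SAP 6.1.4.1 and 8.2.1 to 8.2.4, and delete the conflicting non-response sentence. SAP 8.3 gives no rule for the exploratory PASI and WI-NRS responders, so one line there avoids leaving a gap.
- For B-IGA, use the protocol's multiple imputation. The scale is the same 0 to 4, so the S-IGA steps carry over.
- For PSSI, SI-NRS and PSD, either apply multiple imputation or name one other rule.
- Keep the alternatives as labelled sensitivity analyses, and align the shell footnotes.
- In Section 10, declare and justify every departure from the protocol's multiple imputation.

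The cost is SAP wording plus modest programming to run the existing imputation on B-IGA. Further imputation models are needed only if the sponsor chooses them for the other endpoints. No new data are required.
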